16.5 Handling Steroid or Surgical Interventions

Use of high-dose steroids (e.g., oral, parenteral, injection, budesonide or other sinus steroid irrigations or drops, nebulized steroids administered nasally) or surgical intervention during the study will be recorded and tabulated.

Note: Repeat S8 Sinus Implant at the protocol-specified Day 90 visit does not constitute a high dose steroid intervention.

16.6 Analysis Populations

All analyses will be conducted using the safety population defined as all subjects and sinuses that actually received the S8 Sinus Implant in a target sinus at baseline.

17 STUDY MANAGEMENT

17.1 Ethical Considerations

The rights, safety and well-being of subjects shall be protected in accordance with the ethical principles described in the Declaration of Helsinki. All parties are responsible for ethical conduct of the study in accordance with their respective roles in the investigation. The sponsor and the investigator(s) shall avoid improper influence or inducement of the study subject, monitor, the clinical investigator(s) or other parties participating in or contributing to the clinical investigation.

17.2 Sponsor Responsibilities

Intersect ENT, as the study sponsor, has the overall responsibility for the conduct of the study and will ensure that the study is conducted under the guidance of ICH Good Clinical Practice, Clinical investigation of medical devices for human subjects – Good clinical practice (BS EN ISO 14155: 2011) and other applicable local and federal (e.g., 21 CFR Parts 11, 50, 56, 312 and 812) regulations, including the archiving of essential documents. Qualified personnel who participate in the conduct of this clinical trial will be qualified by education and/or experience to

perform their tasks. Intersect ENT will not use, in any capacity, the services of any person debarred under section 306 of the Federal Food, Drug, and Cosmetic Act in connection with this clinical study.

17.2.1 Training

Sponsor personnel or designee will provide all investigators and sub-investigators with training on use of the S8 Sinus Implant prior to their participation in the clinical study.

The study center staff involved will undergo site initiation and training which will include:

- Study protocol
- Consenting procedures
- Package Insert
- Investigator responsibilities, including reporting requirements
- CRF completion guidelines
- EDC system
- Endoscopic grading scales, recording and video uploading.
- Investigational product accountability procedures
- Protection of subject confidentiality

17.2.2 Protocol Deviation

Any deviation from the requirements outlined in this protocol will be considered a protocol deviation. A protocol deviation that may affect the scientific soundness of the protocol or the rights, safety, or welfare of the patients should be reported to the sponsor and the Institutional Review Board or Ethics Committee as soon as possible. Other deviations are those that occur in direct association with a specific study patient. These include, but are not limited to, deviations from the informed consent process, inclusion/exclusion criteria, protocol-specified procedures and assessments, and investigational product handling and usage. All efforts should be made to avoid any protocol deviation.

17.2.3 Monitor Responsibilities

Study site monitoring will be performed by Clinical Research Associates (CRAs) from sponsor and contract CRAs who will be trained by sponsor. Study sites will be visited regularly to ensure that the study is conducted in compliance with 21 CFR Parts 50, 56, 312, 812, the study protocol and other applicable regulations. Study monitors will also ensure that the data reported in the Electronic Data Capture (EDC) system is consistent with the information found in the subject's medical records and source documents (source data verification). Monitoring will include assessment of the site's overall progress, including but not limited to the site's ability to keep accurate records and to report study related data, including AEs, to the study sponsor in a timely fashion.

17.2.4 Data Management Responsibilities

Data management will be performed by sponsor.

Electronic data capture (EDC)

An EDC system will be utilized to capture study data and compliant with 21 CFR Part 11 and under the guidance of 'FDA Guidance for Industry: Computerized Systems Used in Clinical Investigations'. Data entry will be performed by site personnel after completing an appropriate training. Modifications to the EDC will be made if deemed necessary by the study sponsor.

Data cleaning

The database will be subject to initial inspection for omitted data, gross data inconsistencies, and deviations. Any deficiencies or deviations will be reviewed and any necessary action determined (e.g., data query, communication with the study center).

Intermittent data review will be performed and any discovered errors will be reported to the study site using the electronic query process (as necessary). The study site will be expected to review and complete the query. The data cleaning cycle will be repeated until all data are considered clean.

Data back-up, confidentiality and security

Incremental data back-up will be performed on a regular basis by the EDC system vendor. All media will be stored in a secure location. Passwords will be issued to appropriate personnel to ensure confidentiality and protection of data.

17.2.5 Investigational Product Accountability

An appropriate number of the investigational product, S8 Sinus Implants, will be provided to the study sites. The sites maintain the investigational product in a locked, secure location. Only investigators participating in the study will have access to the investigational product. Dispensing of investigational product will be documented by authorized personnel. Each batch of the investigational product will be assigned a serial/lot number for tracking purposes.

Investigational product inventory logs are maintained by site personnel. These logs are reconciled prior to study closure. Any unused inventory of the investigational product will be returned to sponsor at the direction of the sponsor or at the close of the study.

17.3 Investigator Responsibilities

General responsibilities

- Each investigator is responsible for ensuring that an investigation is conducted per the signed investigator statement (form FDA1572), the study protocol, and applicable

regulations; for protecting the rights, safety, and welfare of study participants under the investigator's care; and for the control of drugs under investigation.

- Each investigator shall, obtain informed consent of each patient to whom the treatment is administered in accordance with provisions of 21 CFR part 50.
- Each investigator is responsible for all applicable IRB requirements under 21 CFR part 56.
- Each investigator and sub-investigators are responsible for disclosure of financial obligations to the sponsor.
- To ensure proper execution of the study protocol, each investigator will identify a study coordinator for this study. Working with and under the authority of the investigator, the study coordinator assures that all study requirements are fulfilled, and is the contact person at the site for all aspects of study administration.
- Each investigator will allow auditing of their clinical investigation procedure(s) by the sponsor or designee.

Control and disposition of the investigational product

An investigator shall administer the product only to patients under the investigator's personal supervision or under the supervision of a sub-investigator responsible to the investigator. The investigator shall not supply the investigational product to any person not authorized to receive it. An investigator is required to maintain adequate records of the disposition of the product, including dates, quantity, and use by patients. All unused product must be returned to sponsor.

Maintenance of study records

Each investigator is required to prepare and maintain adequate and accurate case histories that record all observations and other data pertinent to the investigation on each subject participating in the investigational plan (including information maintained electronically such as digital imaging). The investigator will also maintain original source documents from which study-related data are derived, which may include, but are not limited to:

- Clinic progress notes recording patient's medical history and medications
- Medical charts with operative reports and condition of patient upon discharge
- Medical records regarding AEs, including treatment and clinical outcome
- Results of diagnostic examinations
- Imaging records such as x-rays, CT scans and video-endoscopies and associated reports (hard copy and digital copy of images, as available)
- Notes of phone calls and/or correspondence indicating study center's attempts to follow study patients at the required follow-up visits until their participation in the study is complete or terminated

- Records relating to subject deaths (e.g., death certificate, autopsy report)
- Printouts of source data generated by technical equipment (e.g., CT, endoscopy, MRIs) must be filed with the subject's records.
- Video of endoscopic procedures (screening, treatment and follow up assessments).

An investigator shall retain records required to be maintained for a period of two years following the date a marketing application is approved for the drug for the indication for which it is being investigated. If no application is to be filed, records shall be retained for two years after the investigation is discontinued and FDA is notified. To avoid error, the study site should contact the study sponsor prior to the destruction of study records to ensure that they no longer need to be retained. In addition, sponsor should be contacted if the investigator plans to leave the study center, so that arrangements can be made for the handling or transfer of study records, or if the records are moved to an off-site location.

Required documents from study centers

At a minimum, the following documents will be provided by the study center to the study sponsor:

- IRB study approval letter
- IRB approved informed consent
- fully executed clinical trial agreement (CTA)
- signed statement of investigator (form FDA 1572)
- financial disclosure form for the participating investigator(s)
- curriculum vitae (CV) for the participating investigator(s)
- current medical license for the participating investigator(s)
- principal investigator protocol acknowledgement form

A site may not begin active enrollment of patients until the documentation for the site principal investigator has been provided to sponsor and an initiation visit has been performed.

17.4 Protection of Subject Confidentiality

In all clinical studies, confidentiality of protected health information may be breached due to study-related activities beyond those of routine clinical care. This risk will be minimized by not collecting personally identifying information on CRFs or other study related documentation to be provided to the study sponsor. It is the sponsor's policy to redact any subject's personally identifying information from any documentation sent to Sponsor that inadvertently contains it.

At all times throughout the clinical investigation, confidentiality will be observed by all parties involved. All data shall be secured against unauthorized access. Privacy and confidentiality of information about each subject shall be preserved in the reports and in any publication. Each subject participating in this study will be assigned a unique identifier. All database forms and

source documents sent to the sponsor will be tracked, evaluated, and stored using only this unique identifier.

Investigators will maintain confidential study subject lists identifying all enrolled subjects. The investigators bear responsibility for keeping these lists current and confidential. These lists will not be provided to the study sponsor.

Monitors and auditors will have access to the study screening and enrollment logs and other personally identifying information of study subjects to ensure that data reported in the EDC corresponds to the person who signed the ICF and the information contained in the original source documents. Such personal identifying information may include, the subject's name, address, date of birth, gender, race and medical record number.

The subject's name, medical record number or address will not be recorded in the monitor's visit report or the database. Demographic data that may be recorded include age, race and gender.

Any source documents copied for monitoring purposes by the sponsor will be identified by using the assigned subject's unique identifier in an effort to protect subject confidentiality. All personally identifiable information will be redacted from source documents.

17.5 Study Suspension or Early Termination

The study can be discontinued at the discretion of the investigator or study sponsor for reasons including the following:

- Occurrence of AE unknown to date in respect to their nature, severity, or duration, or the unexpected incidence of known AE
- Obtaining new scientific knowledge that shows that the study is no longer valid or necessary
- Insufficient recruitment of subjects
- Investigational drug presents an unreasonable and significant risk to subjects (sponsor may terminate the study immediately)
- Persistent non-compliance with the study protocol
- Persistent non-compliance with the applicable ethics committee or regulatory requirements

If the study is discontinued or suspended prematurely, the sponsor shall promptly inform all clinical investigators and study centers of the termination or suspension and the reason(s) for termination. The IRB shall also be informed promptly and provided with the reason(s) for the termination or suspension by the sponsor or by the clinical investigator and/or investigation centers. Regulatory authorities and the subject's physicians may also need to be informed, if deemed necessary.

17.6 Site Closeout

At the time of the site close-out visit, the monitor will have ensured all outstanding study documents are reconciled, the investigator's files are accurate and complete, have reviewed record retention requirements with the investigator, made a final accounting of all study supplies, and ensured that all applicable requirements are met for the study (this visit will be conducted according to the study sponsor's SOP for close-out visits). Any specific observations and actions made at this visit may be documented in a final report.

17.7 Quality Assurance and Supervision by Authorities

All documents and data shall be produced and maintained in such a way to assure control of documents and data to protect the subject's privacy as far as reasonably practicable. The sponsor and representatives of the FDA or other regulatory authorities are permitted to inspect the study documents (e.g., study protocol, CRFs, and original study-relevant medical records/files) as needed. All attempts will be made to preserve subject confidentiality.

The study centers are subject to audit by study sponsor personnel or designee for protocol adherence, accuracy of CRFs and compliance with applicable regulations. The sponsor will communicate to the sites any patterns of non-compliance. The sponsor will work with the sites to determine any necessary corrective action, as applicable. The sponsor will continue to monitor sites until compliance has been secured. If the site continues to display non-compliance, more serious action may be taken by the sponsor. The study protocol, data-recording procedures, data handling and study reports are subject to an independent clinical Quality Assurance audit by sponsor, its designee, or health authorities.

Approved informed consent form: protection of study subjects

An IRB must review and approve an ICF specific to this study. Sponsor will provide an example ICF. The site, to meet specific requirements, may modify this example ICF; however, the ICF must contain all of the elements required by sponsor. IRB approved ICF and renewed approvals as appropriate will be maintained by the site for the duration of the study. The original, signed and dated ICF for each subject should be maintained by the site for monitoring.

Subjects will be informed both verbally and in writing (i.e., ICF) about the nature of the study, the anticipated risks and benefits involved and the discomfort to which they will be exposed. They will be instructed about their right to discontinue their participation at any time without prejudice or jeopardy to future medical care. They must confirm consent in writing prior to any screening procedures. A copy of the informed consent form will be provided to the subject.

Institutional review board approval

IRB approval of study protocol and ICF is required prior to study commencement under 21 CFR Part 56. Investigators must also obtain renewal of IRB approval throughout the duration of the study. Investigators are responsible for fulfilling any conditions of approval imposed by the

reviewing IRB, such as regular reporting, study timing, etc. Investigators will provide the study sponsor with copies of such approvals and reports.

Other investigator reports

Investigators are responsible for notifying the sponsor of the following:

Type of Notification	Timeline
Withdrawal of IRB Approval	Within 24 hours of becoming aware
Informed Consent not Obtained	Within 24 hours of becoming aware

Notifications must identify subjects using the unique study identifier to protect subject's confidentiality.

17.8 Final Clinical Study Report

A final clinical study report (CSR) will be prepared by the study sponsor and provided to the regulatory agency.

17.9 Publication Policy

At the completion of the study, an abstract reporting the results will be prepared and may be presented at scientific meeting(s). A manuscript may also be prepared for publication in a peer-reviewed scientific journal. The principal investigators may publish results of the study; however, the study sponsor will be allowed 60 days to review the manuscript prior to submission, to ensure protection of intellectual property.

18 APPENDIX

Appendix A. List of medications considered as high-dose steroids

Trade Name (alphabetic order)	Generic Name	Route of Administration
Budesonide Pulmicort Respules	Prednisone (Budesonide) Budesonide	Nasal (e.g., irrigations, rinses)
Dexamethasone	Dexamethasone	Intramuscular Oral
Decadron Dexamethasone	Dexamethasone	Intravenous or oral Nasal irrigations/rinses
Depo Medrol Medrol Medrol Dosepak Methylprednisolone	Methylprednisolone Methylprednisolone Acetate	Oral Parenteral routes (e.g., intra-articular, intra-cervical)
Fluticasone	Fluticasone Propionate Fluticasone Propionate w/Salmeterol	Nasal irrigations
Kenalog	Triamcinolone Triamcinolone Acetonide	Intramuscular Subcutaneous Submucosal
Prednisone	Prednisone	Intramuscular Oral

Note for CRAs, data managers, biostatisticians: The above table is for reference purposes only and not a comprehensive list. Any questionable cases should be reviewed individually.

1.0 INTRODUCTION

This statistical analysis plan (SAP) outlines the data and procedures to be used for assessing the safety and efficacy endpoints in the ENCORE Study conducted by Intersect ENT under protocol P500-0717 entitled “Safety Evaluation of Repeat Placement of the Corticosteroid-Releasing S8 Sinus Implant in Chronic Sinusitis Patients with Nasal Polyps.” Preparation of this analysis plan was based on the protocol version 2.0 dated October 12, 2017. The purpose of this document is to provide further details regarding the analysis plan.

2.0 STUDY OBJECTIVE

To assess the safety of repeat placement of the S8 Sinus Implant when used in chronic sinusitis (CS) patients with recurrent nasal polyps.

3.0 STUDY DESIGN

This is a prospective, non-randomized, open-label, multicenter clinical trial enrolling up to 50 subjects at up to 10 study centers across the U.S. Eligible subjects undergo in-office bilateral placement of the S8 Sinus Implant in the ethmoid sinuses (total of two implants). Subjects return for seven follow-up visits at Days 30, 60, 90, 120, 150, 180 and 365 (see Appendix A Schedule of Assessments). All implants are removed by Day 90. Subjects meeting eligibility criteria for repeat placement undergo repeat in-office placement of the S8 Sinus Implant in each ethmoid sinus with a nasal polyp grade ≥ 1 . All repeat implants are removed by Day 180.

4.0 STUDY ENDPOINTS

4.1 Safety Evaluation

All adverse events (AE) reported by subjects between consent and the Day 365 follow-up visit (end of study) are tabulated. Each AE is evaluated by investigators in terms of seriousness, severity (i.e., mild, moderate, severe), and strength of relationship (i.e., not related, unlikely related, possibly related, related) to study drug, study device, and implant procedure. Any AE that is determined by a participating investigator to be directly related (related and possibly related) to the study drug, study device, and/or implant procedure will be categorized as implant-related.

Note: The occurrence of a diagnostic or elective surgical procedure for a pre-existing condition, unless the condition becomes more severe or increases in frequency, would not be considered implant-related.

4.2 Efficacy Endpoints

Efficacy endpoints comprise both patient-reported and endoscopic endpoints through the Day 180 follow-up visit.

Patient-reported endpoints

- Change from baseline to each time-point (Days 30, 60, 90, 120, 150, 180) in the nasal obstruction/congestion score (scale 0 to 3)
- Change from baseline to each time-point (Days 30, 60, 90, 120, 150, 180) in the Sino-Nasal Outcome Test (SNOT-22) total score (scale 0 to 110), symptom domain scores (scales 0 to 35), and individual symptom scores (scale 0 to 5)

Endoscopic endpoints

- Change from baseline to each time-point (Days 30, 60, 90, 120, 150, 180) in bilateral polyp grade (scale 0 to 8)
- Change from baseline to each time-point (Days 30, 60, 90, 120, 150, 180) in percent ethmoid sinus obstruction (scale 0% to 100%)

4.3 Other Endpoints

Implant delivery success rate

Percentage of successful deployments of the S8 Sinus Implant to the target site per total number of sinuses attempted during the baseline and repeat placement procedures.

Interventions received

Proportion of subjects who received interventions (i.e., steroids or antibiotics for ethmoid sinus obstruction or for other reasons, polypectomy, repeat endoscopic sinus surgery) through Day 365.

Responder rates: Proportion of subjects who were responders as defined by nasal obstruction/congestion and bilateral polyp grade.

Indicated for repeat endoscopic sinus surgery (RESS) based on clinical data: Proportion of subjects who are indicated for RESS based on nasal obstruction/congestion score ≥ 2 and polyp grade ≥ 2 on each side.

Implant status: Proportion of sinuses with implant status of present, absent, or removed.

5.0 ANALYSIS POPULATION

All analyses are conducted using the safety population, which is defined as all subjects and sinuses that actually received the S8 Sinus Implant in target sinuses at baseline/procedure.

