Implant delivery success	Successful deployment of the S8 Sinus Implant to the target site. Deployment is considered successful if the procedure concludes with a successful placement in the target sinus, even if a second attempt is required. Implant delivery success rate is calculated as proportion of successful deployments of the S8 Sinus Implant to the target site per total number of sinuses attempted including the baseline and repeat placement procedures.

Term	Definition
Malfunction	Failure of an investigational medical device to perform in accordance with its intended purpose when used in accordance with the instruction for use or clinical investigation plan. [BS EN ISO14155] Failure of a device to meet its performance specifications or otherwise perform as intended. Performance specifications include all claims made in the labeling for the device. The intended performance of a device refers to the intended use for which the device is labeled or marketed. [21CFR 803]
Nasal obstruction/congestion scale	A 4-point scale defined as follows: 0: No symptoms 1: Mild symptoms, clearly present but minimal awareness and easily tolerated 2: Moderate symptoms, definite awareness of symptoms that is bothersome but tolerable 3: Severe symptoms, hard to tolerate, cause interference with activities or daily living
Percent ethmoid sinus obstruction	Estimated visually based on endoscopic examination on a scale ranging from 0% (no obstruction) to 100% (complete obstruction of the ethmoid cavity by polyps, edema and/or scarring).
Polyp grading scale	Polyps are assessed endoscopically and graded on an 8-point scale ranging from 0 to 4 defined as follows: 0: No visible sinonasal polyps 1: Small amount of sinonasal polyps confined in middle meatus 1.5: Small amount of sinonasal polyps confined in middle meatus with expanded amount of polypoid edema obstructing $\geq 25\%$ of the ethmoid sinus cavity 2: Expanded amount of sinonasal polyps confined in middle meatus 2.5: Expanded amount of sinonasal polyps confined in middle meatus with expanded amount of polypoid edema obstructing $\geq 50\%$ of the ethmoid sinus cavity 3: Sinonasal polyps extending beyond middle meatus but not totally obstructing the nasal cavity 3.5: Sinonasal polyps extending beyond middle meatus with expanded amount of polypoid edema obstructing $\geq 75\%$ of the ethmoid sinus cavity 4: Sinonasal polyps extending beyond middle meatus and completely obstructing the nasal cavity

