9.3 Other Endpoints

Implant delivery success rate

Proportion of successful deployments of the S8 Sinus Implant to the target site per total number of sinuses attempted including the baseline and repeat placement procedures.

Interventions received

Proportion of subjects who received interventions (i.e., sinus-related medications, systemic steroid interventions, surgical interventions) through Day 365.

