16.4 Analysis of Other Endpoints

Implant delivery success rate

Implant delivery success rate will be reported with descriptive statistics. The left and right sides of each patient will be considered independent, and each patient is expected to contribute up to 4 observations: 2 implants at baseline; between 1 and 2 observations during follow-up (maximum of 1 repeat placements in each ethmoid sinus).

Interventions received

All interventions received for ethmoid sinus obstructions will be tabulated and reported with descriptive statistics.

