7.4 Efficacy and Other Endpoints

Continuous measures are analyzed using descriptive statistics such as means, medians, and SD. and, where appropriate, 95% CI for the mean assuming a normal distribution.

Continuous measures include:

- Nasal Obstruction/Congestion score: Change from baseline to each time-point (Days 30, 60, 90, 120, 150, 180) in the mean score (scale 0 to 3)
- SNOT-22 score: Change from baseline to each time-point (Days 30, 60, 90, 120, 150, 180) in SNOT-22 total score, domain scores, and individual symptom scores. The total score of SNOT-22 is calculated as the sum of all items, and ranges from 0 to 110 with the highest score representing worsening. The following table lists corresponding items and ranges for each symptom domain.

SNOT-22 Domains	Survey Items	Score Range
Rhinologic Symptoms	#1, #2, #3, #6, #21, #22	0–30
Extra-Nasal Rhinologic Symptoms	#4, #5, #6	0–15
Ear/Facial Symptoms	#2, #7, #8, #9, #10	0–25
Psychological Dysfunction	#14, #15, #16, #17, #18, #19, #20	0–35
Sleep Dysfunction	#11, #12, #13, #14, #15	0–25

- Bilateral Polyp Grade: Change from baseline to each time-point (Days 30, 60, 90, 120, 150, 180) in bilateral polyp grade (scale 0 to 8), which represents a sum of left and right sides. The bilateral polyp grade for a given patient is set as missing if the grade for one side is missing.
- Percent Ethmoid Sinus Obstruction: Change from baseline to each time-point (Days 30, 60, 90, 120, 150, 180) in percent ethmoid sinus obstruction (scale 0% to 100%). Percent ethmoid obstruction scores on left and right sides are averaged for each subject at each time point. The results for a given patient is set as missing if the score for one side is missing.

Categorical measures are analyzed as counts, rates, proportions and frequencies. Where it is appropriate, 95% CI (computed using the exact method) and p-values will be presented.

Categorical measures include:

- Implant delivery success rate: Proportion of successful deployments of the S8 Sinus Implant to the target site per total number of sinuses attempted including the baseline and repeat placement procedures. Implant delivery success rate at Baseline, Day 90 and Baseline & Day 90 combined will be presented.

- Interventions received: Proportion of subjects who received interventions (i.e., sinus-related medications, systemic steroid interventions, and surgical interventions) through Day 365.

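### A single received-implant population for all analyses conflicts with the attempted-sinus denominator for delivery success and leaves subjects with no implant placed out of the AE incidence tables

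*SAP*

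**What the plan says.** **Population.** SAP 5.0: "All analyses are conducted using the safety population, which is defined as all subjects and sinuses that actually received the S8 Sinus Implant". Receipt is judged at baseline. Protocol 16.6 likewise uses one safety population for every analysis, "defined as all subjects and sinuses that actually received the S8 Sinus Implant in a target sinus at baseline". Both restrict sinuses as well as subjects, and neither lists an exception.

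**Delivery success.** Protocol section 3 defines success by how the procedure ends: "Deployment is considered successful if the procedure concludes with a successful placement in the target sinus, even if a second attempt is required". Protocol 9.3 counts successes "per total number of sinuses attempted including the baseline and repeat placement procedures", and SAP 4.3 counts them "per total number of sinuses attempted during the baseline and repeat placement procedures". Protocol section 3 and SAP 7.4 give the same denominator. SAP 7.4 adds: "Implant delivery success rate at Baseline, Day 90 and Baseline & Day 90 combined will be presented".

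**Adverse events.** SAP 4.1: "All adverse events (AE) reported by subjects between consent and the Day 365 follow-up visit (end of study) are tabulated". SAP 4.1 also classes an AE related or possibly related to the implant procedure as implant-related. SAP 7.5 promises incidences and percentages through Day 365 and full listings of every AE. Under Protocol section 3, subjects are enrolled when they sign consent.

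**The concern.** At baseline, a sinus enters the population by receiving an implant, and it counts as a success when the procedure ends with the implant placed. These are almost the same event. A delivery rate computed in that population cannot show baseline failures, which are what the endpoint is meant to count. Two of the three rates promised in SAP 7.4 (baseline and combined) therefore depend on which sentence the programmer follows, and neither document says which prevails.

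The same rule also affects safety reporting. A subject in whom placement was attempted and failed on both sides has had the topical or local anaesthesia and the insertion manoeuvres whose risks Protocol 15.3 lists. That subject is outside the safety population, and so outside the AE incidence tables. Consented screen failures are outside it too, although SAP 4.1 starts AE tabulation at consent. In a study whose only objective is safety, exposure to the procedure should be enough to count.

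**Working it through.** **Inputs from the documents.** 50 subjects with two sinuses each give 100 baseline implants. SAP 7.2 expects 85 repeat placements at Day 90. Its total reproduces: 100 + 85 = 185 procedures. SAP 7.4 calls for exact confidence intervals for categorical measures, so Clopper-Pearson intervals are used.

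**Assumptions.** The documents give no delivery failure rate. Final failure per sinus, p, is set at 1%, 2% and 5%, the same at baseline and Day 90. All 50 subjects are attempted on both sides, so f = 100p baseline sinuses fail. All 85 repeat attempts are in sinuses that received an implant at baseline.

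**Delivery success.**

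- Baseline: attempted rule (100 − f)/100; literal population rule (100 − f)/(100 − f) = 1 for any f.
- Combined: attempted rule [(100 − f) + 85(1 − p)]/185; literal rule [(100 − f) + 85(1 − p)]/[(100 − f) + 85].

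| p | Baseline, attempted (95% CI) | Baseline, literal (95% CI) | Combined, attempted | Combined, literal |
|---|---|---|---|---|
| 1% | 99/100 = 99% (94.55–99.97) | 99/99 = 100% (96.34–100) | 183.15/185 = 99.0% | 183.15/184 = 99.5% |
| 2% | 98/100 = 98% (92.96–99.76) | 98/98 = 100% (96.31–100) | 181.3/185 = 98.0% | 181.3/183 = 99.1% |
| 5% | 95/100 = 95% (88.72–98.36) | 95/95 = 100% (96.19–100) | 175.75/185 = 95.0% | 175.75/180 = 97.6% |

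The combined rate is inflated by 0.5, 1.1 and 2.6 percentage points. The Day 90 rate is not forced to 100%, because the population conditions only on receipt at baseline.

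The two rules differ only if at least one baseline sinus fails. Protocol 16.4 says of this endpoint: "The left and right sides of each patient will be considered independent". On that basis the chance is 1 − (1 − p)^100 = 63%, 87% and 99%.

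**AE incidence tables.** A subject leaves the tables only if neither side received an implant.

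- Independent sides: expected number of such subjects 50p² = 0.005, 0.02, 0.125. Chance of at least one, 1 − (1 − p²)^50 = 0.5%, 2.0%, 11.8%.
- Sides that always fail together (an extreme upper bound): expected number 50p = 0.5, 1, 2.5. Chance of at least one, 1 − (1 − p)^50 = 39%, 64%, 92%.

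If one such subject has the only case of some event, the table shows 0/49 = 0% (95% CI 0–7.25) instead of 1/50 = 2.0% (0.05–10.65). If that subject has a procedure AE and three other subjects also have AEs, it shows 3/49 = 6.1% instead of 4/50 = 8.0%.

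**The case against.** The strongest reply is that the specific text governs the general. The attempted denominator is stated four times across the two documents, and SAP 6.2 anchors baseline on the first placement attempt, so the SAP already separates attempt from receipt. An analyst would probably use attempted sinuses. This largely stands: what remains of the delivery point is a missing exception clause. A reader might infer that the study will report 100% baseline delivery. The documents do not support that. Even on the literal reading the figure is not strictly guaranteed, because an implant released into the sinus but not in place when the procedure ends could count as received yet unsuccessful.

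A second reply is that a treated-subjects safety population is a recognised choice and that treatment-emergent events are defined relative to treatment. That is fair as a general rule. Here, however, the plan treats the procedure as a source of implant-related events, and SAP 4.1 sets a wider scope than the population rule allows. A reader might also infer that every failed placement removes a subject, or that AE data disappear. Neither follows. Under the protocol wording, one implanted side keeps the subject in. AEs are recorded from consent (Protocol 14.1) and listed in full (SAP 7.5).

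Third, the size rests on assumed failure rates. Eligibility screens for implant access, the implant can be repositioned after placement, and a second attempt counts as success; all of these lower final failure. The denominator of 50 is also unsettled: the protocol plans 50 treated subjects, while the SAP speaks of enrolling up to 50. If an unimplanted subject does not count toward 50, the single-event comparison becomes 0/50 against 1/51 = 2.0%, which is practically the same.

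Finally, the contents of the table mock-ups in SAP Appendix B are not available for this review and may already show the right denominators. Even so, the conflicting sentences in the two documents would still need to be reconciled.

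**Conclusion.** The conflict is real and minor. As written, one received-implant population covers all analyses. It contradicts the attempted-sinus denominator for delivery success, and it leaves subjects who had the procedure but no implant on either side out of the AE incidence tables. For delivery success the attempted denominator is very probably intended. If the population sentence were followed instead, the baseline rate would be essentially 100% and the combined rate would be 0.5 to 2.6 points too high at an assumed 1% to 5% failure per sinus. For AEs, the chance that any subject is affected is about 0.5% to 12% at those rates with independent sides. The 39% to 92% range needs complete left-right correlation and should be read only as an outer bound. Confidence is high that the text conflicts. It is only moderate that reported results would change, because the table mock-ups could not be checked.

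**What to change.** - **Delivery success.** State in SAP 5.0 and 7.4 and in Protocol 16.4 and 16.6 that this endpoint uses all sinuses in which placement was attempted, at baseline and at Day 90, as an exception to the safety-population rule.
- **AE incidence.** State in SAP 5.0 and 7.5 and in Protocol 16.2 and 16.6 that the AE incidence tables include all subjects in whom placement was attempted at baseline.
- **Never-attempted subjects.** Report AEs in consented subjects with no placement attempt separately; a listing or a short table is enough to meet SAP 4.1.
- **Efficacy.** Leave these analyses unchanged.

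The cost is a few sentences and at most one small table. The delivery rate may print slightly lower. The endpoint definition implies that attempts are recorded, but no CRF field is visible in the documents, so the sponsor should confirm that failed attempts are captured.
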